#### 4.2 Risk management and mitigation

No negative effects are expected on the health of users related use of the technology platform. The hardware devices used are commercial devices and CE certified and/or safety certification, the applications for older people and caregivers will be loaded on the hardware held by the users.

Technological dependence, especially on AI devices, represents a major ethical dilemma in today's society and scientific community. In order to limit the risk, the European Commission's international programmes have introduced guidelines for conducting studies that require the introduction of a new technology, called Responsible Innovation. The core principles of Responsible Innovation are also applied within the engAGE project. In particular, a strategy underlying the prevention of technological dependence is the inclusion of different actors around the older people, in the process of acquiring skills and daily use of technology. In this way, technological solutions such as those proposed by engAGE, respond to the definition of socio-technological system rather than technological, since they are placed in a care context that does not involve the replacement of the caregiver but stimulates the user to play a leading role in the management of their health.

The services proposed are intended to support the maintenance or improvement of cognitive abilities through specific activities and do not replace (in whole or in part) the support from professional services.

During the installation of the technology, moreover, information will be provided to the caregiver about the limits of the technology, which can in no way replace the role of the familiar and formal assistant, but only assist in some activities.

Users who take part in the study will not incur any direct or indirect costs related to the use of the technology platform. The platform will be provided to the subjects by the Experimental sites and must be returned to the research team at the end of the trial.

#### 4.3 Data Management

In the case of the engAGE project, a critical area of security is the servers (cloud or on-premises) where the solutions will be deployed, or on which data will be stored. These need to be provided with physical and logical protection. Also, the communication network architecture should consider implementing mechanisms of comprehensive network protection against intrusion such as IPS (Intrusion Prevention System), firewall and network antivirus filter. The core system should be placed in a secure area (Secured Zone) excluding the necessary communication modules located in the DMZ (demilitarized zone), enabling data exchange with engAGE services, devices, and components. In the case of communication via an external network, strong mechanisms are required to guarantee the protection of transmitted data, their integrity, confidentiality and non-repudiation (e.g., TLS -Transport Layer Security). Authorization procedures should be implemented specifying who is authorized to access the network and network services - access to services should be possible only for authorized users/devices by providing authentication and authorization mechanisms. Access to individual applications must require a user ID and authentication (password, authentication certificate). The application functionality available to individual users should be limited by the user's rights. The system architecture should include solutions that eliminate or significantly reduce the system's vulnerability to attacks as recommended in the Open Web Application Security Project (OWASP).

Different types of data will be collected in the engAGE project:

- Credentials usernames, passwords, email addresses and similar security information used for authentication and account access in different services of the platform (i.e., Tellu web and Dialog app, Fitbit application, Memas, Pepper tablet, etc.);
- personal data such as first name, last name, gender, age, weight, height, email address, contact address, phone number, etc. of older adults' end-users in different services of the platform;
- answer to specific questions in self-assessment questioners (Memas);
- games scores from the Pepper applications;
- measurements and monitored parameters such as weight, heart rate, blood pressure, physical activities of older adults' end-users gathered through the monitoring infrastructure in the Tellu platform storage;
- historical data about the above measurements and monitored parameters for training and using ML algorithms for each older adult in the ML service.

In the engAGE testing and evaluation phase, the following data will be processed:

- information and results from questionnaires;
- cognitive games scores
- historical data for each end-user collected measurements;
- any information the end-users decide to share through discussions / interviews as well as data providing feedback from trials.

In the designed solution, data will be transferred using REST APIs. To secure data transmission, it is recommended to use the HTTPS protocol using the TLS protocol to encrypt data especially for web applications. This approach gives the opportunity to use three levels of data access security. Security of an access to health data can be also achieved based on the use of a firewall with appropriate security rules. In engAGE different types of databases are used for storing data. These database

servers give the option of encryption at several levels, and provide flexibility in protecting data from disclosure such as:

- password storage encryption database user passwords are stored as MD5 hashes;
- encryption for Specific Columns allows certain fields to be stored encrypted; this is useful if only some of the data is sensitive;
- data partition encryption an entire file system partition can be encrypted on disk, and decrypted by the operating system;
- encrypting data across a network SSL connections can encrypt all data sent across the network: the password, the queries, and the data returned.

engAGE consortium will store and keep data for as long as necessary to fulfil the project purposes unless otherwise required by law and the contract for the project. During the research and development phases of the project's lifetime phases each **technical partner** will provide its own infrastructure for hosting the developed services and storing the associated data.

#### 4.3.1 Storage in Tellu premisses

Data stored in Tellu's TelluCare cloud platform is kept to the minimum required to use a mobile app connected to this platform. Firstly, TelluCare includes an authentication broker, where user names and passwords are stored in an encrypted database. The authentication broker is an instance of Keycloak, an Open-Source state-of-the-art Identity and Access Management application following the latest industry standards in security. No other service has access to this information, as all authentication must be done through the web interface or API of the broker, and it will only give out time-restricted tokens which can be used to access Tellu APIs. Secondly, a Dialogg user associated to an ID in the authentication broker must be registered to use the mobile app. A name and email address can be registered here, but these need not be real. An audit log is kept, to show when a user has access data in TelluCare. No other information will be stored in TelluCare – specifically, no sensor measurements, such as from Fitbit, will be stored here.

Tellu will use their production cloud deployment in engAGE. This is hosted in Microsoft's Azure cloud platform, with a data centre located in Norway. This is the same cloud deployment which is used for real patient data, following the high security requirements of ISO 27001, but with a separate network domain set up for engAGE. Tellu is ISO 27001 certified, and all data storage in engAGE is handled according to this standard. Access to Tellu's Azure nodes is through VPN and only available to key Tellu personnel. As all data is encrypted, access to the databases running in Azure does not give access to the data itself.

No data is stored in the mobile gateway app, except for the time-limited refresh tokens used to access TelluCloud and Fitbit services, and these are stored encrypted (so that the user does not need to log in each time). The app does not have access to user credentials for these services, as authentication is done by the user in the secure web interfaces of the respective service, which is not inside or accessible to the app. The app only gets the tokens issued by the authentication services. For Fitbit, this token is used to get access to collected data from the Fitbit API. This data is transmitted to the engAGE MLCDA service for processing and storage.

#### 4.3.2 Storage in INRCA premisses

INRCA will keep all written test recordings (filled in moderator's guide, informed consent, demographic & and all survey results) in electronic format (audio recordings an word/excel files) in a secured repository. All the physical data (papers of questionnaires, interviews, demographics) will be kept on a locked drawer.

All data acquired through third part systems, such as Fitbit (see below) are subject to the policies of the third part, which have been clarified to all participants.

#### 4.3.3 Storage in Karde premisses

In the engAGE project, we will collect anonymous end-user data which will be delivered to the data handling partners ('behandlingsansvarlig') partners technical University of Cluj-Napoca (coordinator, Romania) and INRCA (responsible for end user studies, Italy) for overall aggregated analyses and conclusions for improvement of the technology, seen from the end user perspective.

These data will concern only the end user experience that report the engAGE prototype's usability and accessibility in different stages of maturity of the engAGE software/hardware. No information of diagnoses or medication concerning MCI or dementia will be asked for or stored.

The end user participants will therefore be shielded from any intrusive or unnecessary questions as far as the project's (one and only) technology goal is concerned.

The Norwegian research will only concern levels of everyday function and IADL (i.e., practical level of performance ability concerning activities of daily living and self-sufficiency), connected to the technology of the engAGE project. Data not directly connected to the improvement of the engAGE technology, will not be posed.

Karde AS will be the responsible partner for collecting and creating the aggregated Norwegian data for the consortium. Following aspects cover our data management approach:

- All individual data sheets of the end-user participating in the tests and trials, will be coded and not include any information that allows to identify the individual participant.
- Karde AS or Tellu AS do not keep these data over time neither electronic nor on paper.
- Karde's or Tellu's data sheets with interview data will be destroyed at the end of the project.

Our understanding is that the project coordinator and other project participants will follow all necessary rules and guidelines for data management concerning the project's data.

Contact person for data management in Karde AS is [name] ('personvernombud', appointed for Karde AS by the Norwegian Data Protection Authority). She will act as the contact person for data management for both Norwegian project partners.

#### 4.3.4 Storage in TUC premisses

TUC stores historical data for the ML service in its premises in Cluj-Napoca, Romania. TUC has allocated a specific state of the art server for storing engAGE data. This server is isolated from other research and development activities done in other projects implemented by TUC, it is dedicated to engAGE. Physical security measures for protecting the data stored on the server:

- the server is in a secured area with fire protection, proper ventilation and cooling;
- only authorized personnel have access to the server room (TUC team researchers);
- access in the server room is done based on secure key cards, which are kept in a locked office when not used;
- the server room has an allocated alarm system which is permanently activated when authorized personnel are not in the room. Passwords for alarm system are known only by engAGE TUC personnel;
- the server has backup batteries for power outage.

Logical security measures for data protection on TUC server:

- The server HDDs use RAID techniques for backing up data in case of one HDD failure;
- the operating system (OS) is a Linux kernel is protected through authentication and authorization. Only engAGE TUC personnel has the credentials for accessing the OS level services;
- the communication network uses mechanisms of comprehensive network protection against intrusion such as: IPS (Intrusion Prevention System), firewall and network antivirus filter;
- remote access to the server is possible only through secured VPN connections and only TUC personnel from the project have credentials and details how to access it;
- the MLCDA service is isolated at the OS level using Docker containers; the DB servers deployed on the physical server are protected against intrusions using password authentication. DB passwords are known only by TUC engAGE personnel.

The personal data collected by each of the end-user organizations (HUG, INRCA, KARDE) in trials must be securely stored on local hard drives as password protected files under specific authorization measures; the physical forms should be kept in locked, fireproof drawers. Data will be pseudonymized – Identity of data subjects will be concealed by replacing their names with codes; access to pseudonymized data will be given only to authorised researchers at the pilot sites; all data that is included in internal reports, tables, internal communications, public deliverables will be anonymized and will not contain identifiable details; any questionnaires or input acquired from voluntary participants in the scope of the engAGE project will be handled in the strictest confidence;

#### 4.3.5 Storage at HUG

HUG will keep all written test recordings (filled in moderator's guide, informed consent, demographic and all survey results), scanned when required, in a protected institutional area with institutional access policies restricted to the lab involved in the project. All the electronic data (audio/video recordings, filled excel spreadsheet) will be kept on a secured repository.

All data acquired through third part systems, such as Fitbit (see below) are subject to the policies of the third part, which have been clarified to all participants.

All collected data will be destroyed 5 years after the end of the project and will be used only in the scope of the project to evaluate the system for scientific purpose.

#### 4.4 Ethics

The principles of the Declaration of Helsinki and Good Clinical Practice guidelines will be adhered to. Participants in this study provide written informed consent.

Personal data collected during the trial will be handled and stored in accordance with the General Data Protection Regulation (GDPR) 2018. Use of the study data will be controlled by the principal investigator. All data and documentation related to the trial will be stored in accordance with applicable regulatory requirements and access to data will be restricted to authorized trial personnel.

The acquisition of informed consent from people with cognitive impairment is a long-debated issue.

Although degenerative neurological syndromes over time lead to a progressive decline in cognitive functions and with them the ability to express valid consent, the diagnosis of Alzheimer's disease or dementia does not in itself lead to the loss of this ability. The legal capacity and the capacity to act remain, unless proven otherwise, from the age of majority until the death of the person. Only a judicial

measure can protect the person with dementia who is unable to provide informed consent by appointing a legal representative.

The person with dementia can maintain decision-making skills about some or many aspects of their life and health for a long time.

From a neuropsychological point of view, the impairment of executive functions (abstraction ability, problem solving, judgment and criticism, planning, farsightedness, 'decision making' ...) is directly proportional to the decrease in capacity both in a general sense that in the various fields: health and economic decisions, driving skills, etc. However, these cognitive functions can be spared in the early stages of the disorder (MMSE> 19), unlike others that are affected early, such as memory and orientation.

It is also common clinical experience that, even if unable to understand the contents of a standard "informed consent" form (which must certainly be simplified), the person with dementia is often able to express his/her choices in line with his lifestyle, preferences and values. This underlines the importance of preserving the possibility for potential participants to use their skills to share possible choices.

Informed consent is a legal condition in which a person accepts an action that is proposed to him/her (in our case, active participation in the feasibility study). To be "informed", consent must be based on a full understanding of the action itself and the implications it can bring. This implies that:

every effort must be made to guarantee and respect any residual capacity for autonomous decision, considering consent as an instrument through which the subject realizes his autonomy.

The autonomy of the subject requires that all information be understood the person's consent presupposes his/her ability to choose freely on the basis of his preferences, moral values, life stages and circumstances.

It is therefore necessary first of all to inform the person with dementia, adapting the information to the cognitive abilities of the same, making every effort so that the patient can directly or indirectly communicate his preferences. With this in mind, the opinion of family members, for example, may be requested, but considered secondary to that of the patient.

The person with dementia who gave his/her informed consent to participate and is not comfortable during the sessions may at any time withdraw from the trial without any consequences.

In the specific case of our study, neither serious harmful effects on the person with dementia are foreseeable nor is there bad faith in our treatment proposal. On the contrary, literature studies demonstrate the potential benefits of the proposed intervention.

With this in mind, we proceed to ask the person with dementia to provide their informed consent to participate and we strive to:

- ensure that he/she clearly understands the content of the information sheet and the consequences of his/her participation;
- create the best conditions in which he/her can ask questions and express his/her will;
- monitor throughout the course of the trial the persistence of his/her willingness to participate.

During the clinical interview, the contextual assessment of the ability to express an autonomous choice will be carried out, assessing the presence of:

- Ability to express a choice;
- Ability to understand information relating to consent;
- Ability to give due weight to the situation and its possible consequences;
- Ability to use information rationally.

In the event that this evaluation gives a positive result, informed consent will be acquired from the person him/herself. Time and effort will be devoted to providing correct and full information, the information sheets and the consent form will be read together with the person with dementia and their caregiver, the opportunity to ask questions will be given and the best conditions will be created to make a decision. An additional opinion will be requested from the main and reference caregiver on whether or not the person with dementia should participate in the project, what his/her wishes and feelings about participation may not have been expressed. If the subject then shows signs of dissent before and during each training session or shows behaviours that suggest that he/she is no longer willing to participate, the sessions will be terminated and the consent will be automatically withdrawn.

For people unable to express valid consent, on the other hand, European Regulation 536/2014 identify in the figure of the legally designated representative (support administrator) the person who must be involved in the information process and from whom informed consent must be obtained. Even in this case, however, the will of the person directly concerned to participate in the "double consent" mode will be tested.

The equipment needs electric power. However, the tablet and the mobile router are rechargeable and low power consumption. The user will be informed on how much electric power is supposed to be consumed and how much it will cost to him/her. No refund to the end user is planned.

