The field trial is a pilot study, that is, a small-scale study, conducted mainly to control whether and how the developed services are perceived useful and usable. The defined qualitative and quantitative key performance indicators (KPI) will be evaluated and used to assess the degree to which engAGE meets the elders' needs, wishes and priorities in all trial sites (i.e. achieving better engagement, better social interaction, and accurate measurement of cognitive decline based on machine learning techniques). The measurements collected from the real-life trials will be elaborated and evaluated, to assess the ecosystem performance and validate the success of the project-developed technologies. The field trial will conduct only a partial evaluation of the effectiveness of services in relation to some dimensions of cognitive status of older people with MCI.

In the following scheme (Fig. 2) the study design is summarized. A certain number of people are recruited for the study, then those who do not meet the criteria or decline the participation are excluded. The remaining participant are randomly assigned to the experimentation group or to the control group. In randomization technique based on a single sequence of random assignments is used. A list of random numbers generated by the computer is used and subject is assigned a number based on their order of inclusion in the study. According to this technique, the 80 subjects are randomly assigned to the

experimentation group or to the control group. Then, for both the groups it has to be taken note of who loose follow up, discontinued intervention, and/or are excluded from analysis.

Figure 2. Field trial - study design

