#### 3.4 Outcomes

In this section the outcomes measured throughout the field trials are reported. The main focus of the engAGE project, and so of the field trial, is the perceived stability of cognitive capabilities of people with MCI. In second place, the acceptance and the usability of the platform, as well as the caregivers' benefits have to be assessed. Thus, the outcomes are the following:

- PRIMARY END USERS (SMCI):
  - Primary outcome: perceived stability of cognitive status (MAC-Q)

- Secondary outcomes: Adherence to intervention, wellbeing, quality of life, acceptance and usability, cost-benefit analysis
- SECONDARY END USERS (INFORMAL CAREGIVERS):
  - Reduction/stability of informal caregiver's burden
  - Improvement of well-being, psychological status
  - Acceptability, usability and affordability of the solution
- TERTIARY END USERS (FORMAL CAREGIVERS):
  - Improving quality of work.

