#### 3.6 Description of the intervention

In this section, the intervention is descripted in details.

The experimental group (EG) use the engAGE system in two different settings: at healthcare organization and at home. At the healthcare organization, the primary end user (SMCI) interacts with Pepper. The interaction **at healthcare organization** is supervised by tertiary end users (formal caregivers, i.e., occupational therapist, psychologist, nurse, etc...) and includes the following activities: dialoguing with the robot, storytelling, drama play, cognitive and physical games. This interaction is planned to last about **1 hour and to be scheduled twice a week for 6 months**. **At his/her home**, the older user interacts with the tablet and is supervised by the relative informal caregiver. Also in this case, the user plays cognitive and physical games installed on MEMAS app. Even this activity is **performed for 0,5 hour, every day for 6 months**. Throughout the whole period of experimentation (unless (s)he decides otherwise), the older user wears the smartwatch that measures his/her physiological parameters and the steps. Any activity performed by the seniors is assigned by formal caregiver and can be personalized taking into account the user's abilities (difficulty levels of the games), lifestyle (reminding and monitoring services), and social interactions.

The activities performed by the user through the engAGE system are schematized in the figure below:

Figure 3. Summary of engAGE activities

Table 7. Games of the Engage platform

Name of games	Description
	Familiar games

Crossword	Helps with long term memory, having	★: easy level (infinite tips)			
	definition or pictures.	★★: medium level (limited tips)			
Karaoke	Helps SMCI to have fun while singing songs they already know (train memory without noticing).	★★★: hard level (no tips)			
Memory card	Helps with spatial memory, which can help SMCI to find lost objects in the future.				
Sudoku	Helps with visual memory, using numbers instead of letters can be easier and more enjoyable. It's an appreciated game for SMCI.				
2 differences game	Helps to stay focus, observe, retain the information to seek.				
Quizzes					
Picture quiz	Find the celebrities/animals behind.				
	$\star$ : picture $\star$ $\star$ : pixelated photo $\star$ $\star$ $\star$ :	★: silhouette			

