#### 3.6.1 The control group

The control group (CG) will be given a booklet containing some suggested activities to do at home.

They will be evaluated at T0 and at T6 like the EG.

A first and a final meeting will take place in order to introduce and explain the project to the volunteers, and to show the results collected during the experimentation.

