#### 5.3 Risk-benefit analysis and exit strategy

This study poses little risk to participants however, there are some risks. There is a risk that the elderly person may wish to stop interacting with the technological devices (for example because they do not like the robot). In this case the experiment will be immediately stopped and terminated.

To protect the safety of participants:

- Participants will be informed about the appropriate use of the devices (especially the social robot);
- The researcher will train the participant in the use of the devices and be available in case of problems;

• The technological devices (tablet and mobile connection) will be placed in the participant's home in a configuration that allows them to be used safely.

In the event of adverse events occurring despite the precautions described above (section 5.2):

- Participants will be instructed to press the "off" button on the device or to disconnect it according to the instructions in the user manual;
- Participants will call the researcher, who will assist the participant in case of problems.
- Participants will be able to call the researcher, who will come and ensure that no damage has been caused to the participants or to any other person.

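### Tying the end of sessions to withdrawal of consent is likely to cost the experimental group more T2 outcomes than the control group, and the analysis plan does not deal with the loss

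*Combined protocol and SAP*

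**What the plan says.** Three places bear on what happens to someone who stops.

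- **Section 4.4 (Ethics).** The rule opens "If the subject then shows signs of dissent before and during each training session" and adds a second trigger, behaviour suggesting that the person no longer wants to take part. The consequence of either is that "the sessions will be terminated and the consent will be automatically withdrawn".
- **Section 5.3 (Risk-benefit analysis and exit strategy).** A person may wish to stop interacting with the devices, "for example because they do not like the robot". The text continues: "In this case the experiment will be immediately stopped and terminated". Consent, data and follow-up are not mentioned.
- **Section 3.1 (Study design).** For both groups, a note is to be kept of who is lost to follow-up, "discontinued intervention, and/or are excluded from analysis".

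The arms differ in exposure. Under section 3.6, EG participants have robot sessions planned to last "1 hour and to be scheduled twice a week for 6 months", plus daily tablet use at home. Under section 3.6.1, "The control group (CG) will be given a booklet containing some suggested activities to do at home".

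Table 5 schedules MAC-Q, the primary outcome, at recruitment (R) and T2 only. SUS and UTAUT are scheduled at T1 and T2. Adherence is collected technically. Section 4.1 names descriptive statistics, tests and correlations. It gives no analysis set, no follow-up after stopping and no handling of missing values.

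**The concern.** In section 4.4, ending the sessions and withdrawing consent are a single act. No section provides for a participant who stops using the system but stays in the study for the T2 questionnaires. The most obvious triggers are a reaction to the robot or to a session, and only EG has either. The people missing at T2 may therefore differ systematically from those who remain, and be missing more often from one arm.

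Two results are exposed. One is the MAC-Q comparison of section 3.7, both between groups and within EG. The other is the comparison of T1 with T2 that section 3.1 uses to judge long-term acceptance. Those who stop are well placed to say what did not work, and their later usability answers would be absent.

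**Working it through.** **Step 1. The trial's own figures.** Section 3.1 randomises 80. Table 2 gives EG 20–22 + 20–23 + 8–10 = 48–55, and at least 30 controls. The total is 78–85 at the control minimum, which is consistent with 80 split 50/30. No alpha, power, MAC-Q SD, effect size or dropout allowance is stated, so 80 cannot be rebuilt from a sample-size formula. The sizes below rest on assumptions.

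**Step 2. Where the triggers can arise.**

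| Trigger | Stated consequence | EG | Control |
|---|---|---|---|
| Dissent around a training session (4.4) | Sessions end, consent withdrawn | Yes | No sessions |
| Apparent unwillingness to take part (4.4) | Sessions end, consent withdrawn | Yes | Possible |
| Wish to stop using the devices (5.3) | Experiment ends; meaning for participation not stated | Yes | No devices |

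One trigger of three can apply to a control. More frequent loss in EG is the reasonable expectation; loss in EG alone is not.

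**Step 3. Which outcomes are lost.** T1 is month 3 and T2 is month 6. I take withdrawn consent to mean no later assessment. That follows from the rule, although no sentence says it.

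| Participant leaves | MAC-Q | SUS and UTAUT | Adherence |
|---|---|---|---|
| Before T1 | R only | None | Logged up to stopping |
| Between T1 and T2 | R only | T1 only | Logged up to stopping |

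Adherence is less affected, provided that data already collected are kept. The plan does not say whether they are.

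**Step 4. Shift in the EG mean.** Let a fraction f of EG stop, and let them score g MAC-Q points worse (higher) than completers would. With completer mean m, the full-arm mean is (1 − f)m + f(m + g) = m + fg. The completer mean is therefore better than the full-arm mean by f × g.

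- f = 10%, g = 2: 0.1 × 2 = 0.2 points
- f = 20%, g = 2: 0.2 × 2 = 0.4 points
- f = 20%, g = 4: 0.2 × 4 = 0.8 points

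For comparison, with SD 4 the 95% CI half-width for the between-group difference is 1.96 × 4 × √(1/50 + 1/30) = 1.81. With 20% of EG lost it is 1.96 × 4 × √(1/40 + 1/30) = 1.89. If those who stop would have scored better, g is negative and the shift reverses.

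**Step 5. Effect on the test, from a second model.** Suppose there is no true effect, the fraction d of EG that likes the system least is lost, and liking has correlation ρ with outcome. The bias in favour of EG is ρφ(z_d)/(1 − d) SD, where φ is the standard normal density and z_d its d-quantile. For d = 20% and ρ = 0.5: 0.5 × 0.280/0.8 = 0.175 SD.

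| d | Bias in SD, ρ = 0.2 to 0.5 | Two-sided 5% test rejects (normal approximation) | Simulated Mann-Whitney |
|---|---|---|---|
| 10% | 0.04–0.10 | 5.3–7.0% | 5.4–6.6% |
| 20% | 0.07–0.18 | 6.0–11.2% | 5.6–11.8% |
| 30% | 0.10–0.25 | 6.8–17.0% | 5.8–15.3% |

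With ρ = 0 there is no bias. The simulation used 50 versus 30 before loss and 4,000 runs per setting. Step 4 gives 0.2/4 = 0.05 to 0.8/4 = 0.2 SD, a similar range.

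**The case against.** The strongest reply is that the text supports less than a quick reading suggests. Most of that reply stands.

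- **Loss confined to EG.** A reader might infer this because controls have no sessions. The second trigger in section 4.4 is not tied to sessions, and controls can also withdraw or be lost.
- **Disliking the robot withdraws consent.** Section 5.3 does not say so. Its wording can mean the end of the interaction or the end of participation.
- **Those who stop are dropped from the analysis.** Section 3.1 lists participant-flow categories to be noted in both groups. It does not say that discontinuation leads to exclusion. Recording by group is therefore already foreseen; reasons are not.
- **All usability results come from satisfied users.** SUS and UTAUT are also scheduled at T1, so anyone who stops after month 3 has values for both. An inflation of 6 SUS points (20% stopping, 30 points lower, 0.2 × 30) would need every person who stops to contribute no score, and the documents give no basis for either input.
- **The bias favours EG.** Its direction is an assumption, as is its size. On the values used here the MAC-Q shift lies inside the confidence interval half-width, and the trial describes itself as a pilot with only a partial evaluation of effectiveness.
- **Automatic withdrawal protects people.** Dissent in cognitively impaired participants may be shown by behaviour alone. A remedy that kept collecting data unless the person objected would weaken that protection. This bears on the form of the fix.

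The consent form (Annex 1) and Figure 2 were not in the text available to me, and either may say more. What the reply does not answer is that section 4.4 joins stopping and withdrawal, MAC-Q has no measurement between R and T2, and section 4.1 has nothing to offset the loss.

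**Conclusion.** The point holds in a limited form. Followed as written, the plan loses post-baseline MAC-Q for anyone withdrawn before T2. That loss is likely to be more frequent in EG and related to reaction to the intervention. T2 SUS and UTAUT are lost as well, and T1 values for those who leave before month 3, which weakens the T1–T2 acceptance comparison.

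Size and direction are not knowable from the documents. With 10–20% stopping and scores 2–4 points worse, the EG mean is flattered by 0.2–0.8 points, roughly a tenth to under half of the 1.8-point half-width. This is a shift worth preventing, and not one that by itself would decide the result. It should be corrected because the remedy is mainly wording and the lost values cannot be recovered afterwards.

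**What to change.** 1. Reconcile sections 3.1, 4.4 and 5.3 on whether stopping the sessions means leaving the study. Leave the rules on when sessions stop as they are.
2. Add that a participant who stops is asked, separately and without pressure, whether they agree to the T2 questionnaires, and to SUS, UTAUT and the interview at the time of stopping. Data collection continues only with an explicit yes; otherwise the withdrawal stands. If Annex 1 already offers this choice, carry it into these sections.
3. In section 4.1, state that all participants with data are analysed in the group to which they were randomised, and how a missing T2 MAC-Q is handled. The f × g shift above would serve as a simple sensitivity analysis.
4. State what happens to data collected before withdrawal, including the adherence logs.
5. Report stops by arm, with reasons.

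The cost is protocol and analysis wording, one extra consent option that needs ethics review, and a few assessments in people who have stopped. At 10–20% of 50 that is at most 5–10 people, fewer if some decline. Section 3.1 places the final evaluation after the system is removed, so it does not depend on current use.
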